Appendix D

Modified Medical Research Council Dyspnoea Scale (mMRC): this scale goes from 0 to 5

▶ MODIFIED MRC DYSPNEA SCALE ^a		
PLEASE TICK IN THE BOX THAT APPLIES TO YOU ONE BOX ONLY Grades 0 - 4		
mMRC Grade 0.	I only get breathless with strenuous exercise.	
mMRC Grade 1.	I get short of breath when hurrying on the level or walking up a slight hill.	
mMRC Grade 2.	I walk slower than people of the same age on the level because of breathlessness, or I have to stop for breath when walking on my own pace on the level.	
mMRC Grade 3.	I stop for breath after walking about 100 meters or after a few minutes on the level.	
mMRC Grade 4.	I am too breathless to leave the house or I am breathless when dressing or undressing.	
^a Fletcher CM. BMJ 1960; 2: 1662.		

Appendix E

Saint George Respiratory Questionnaire (SGRQ)

IPF-Specific Version of the SGRQ

J Yorke, PW Jones, J Swigris

Symptoms Component

The original SGRQ contains 8 items in the Symptoms component. Items 6 and 8 were removed due to missing data. The remaining 6 items displayed disordered thresholds and required adjacent response categories to be collapsed. All of the 6 items displayed good-fit to Rasch model and were retained. The format for the SGRQ-I symptoms component is detailed below. Figure E1 displays the item map for this component.

SGRQ-I Symptoms Component

Item 1: I cough:

- | | |
|--------------------------|-------------------|
| 2 = Almost every day | (new weight=80.6) |
| 1 = Only with infections | (new weight=40.2) |
| 0 = Not at all | (new weight=0) |

Item 2: I bring up phlegm:

- | | |
|--------------------------|-------------------|
| 2 = Almost every day | (new weight=76.8) |
| 1 = Only with infections | (new weight=41.4) |
| 0 = Not at all | (new weight=0) |

Item 3: I have shortness of breath

- | | |
|--------------------------|-------------------|
| 2 = Almost every day | (new weight=87.2) |
| 1 = Only with infections | (new weight=50.3) |
| 0 = Not at all | (new weight=0) |

Item 4: I have attacks of wheezing

- | | |
|--------------------------|-------------------|
| 2 = Almost every day | (new weight=86.2) |
| 1 = Only with infections | (new weight=51.0) |
| 0 = Not at all | (new weight=0) |

Item 5: How many attacks of chest trouble have you had?

- | | |
|-------------------|-------------------|
| 1 = more than one | (new weight=66.2) |
| 0 = none | (new weight=0) |

Item 6: How often do you have good days?

2 = every day (new weight=93.3)

1 = a few days (new weight=51.2)

0 = none (new weight=0)

Activities Component

The original SGRQ contains 16 items in the Activity Component. All items were analysed using Rasch analysis.

Items 1, 5, 10, and 15 demonstrated the least fit to the Rasch model ($\chi^2 p < 0.05$) and were removed. A further two items (8 and 9) demonstrated a high logit value (i.e. severity) and were removed to improve the targeting of the component (item 8 logit = 4.2, item 9 logit = 5.7) (Figure E2).

SGRQ-I Activities Component

Activities that make you short of breath

Item 1: Washing or dressing

1 = true (new weight=82.2)

0 = false (new weight=0)

Item 2: Walking in the house

1 = true (new weight=80.2)

0 = false (new weight=0)

Item 3: walking outside on ground level

1 = true (new weight=81.4)

0 = false (new weight=0)

Item 4: Walking up a flight of stairs

1 = true (new weight=76.1)

0 = false (new weight=0)

Item 5: Playing sports or active games

1 = true (new weight=72.1)

0 = false (new weight=0)

Activities that might be affected by your breathing problem

Item 6: Household chores take a long time

1 = true (new weight=70.6)

0 = false (new weight=0)

Item 7: Walking up one flight of stairs, I have to go slowly or stop

1 = true (new weight=71.6)

0 = false (new weight=0)

Item 8: If I hurry or walk fast, I have to slow down or stop

1 = true (new weight=72.3)

0 = false (new weight=0)

Item 8: Breathing problems makes it difficult to do things such as walking up hills

1 = true (new weight=74.5)

0 = false (new weight=0)

Item 12: Breathing problem makes it difficult to do things such as very heavy manual labour

- 1 = true (new weight=63.5)
0 = false (new weight=0)

Impacts Component

The original SGRQ contains 26 items in the Impacts Component, the SGRQ-I retains 18 of these. Items 17, 18, 19, and 20 had high levels of missing data and were removed. The remaining 23 items were analysed using Rasch analysis. Item 2 displayed disordered thresholds. This was corrected by rescored the item; it now contains 2 response categories. Three items did not fit the Rasch model ($\chi^2 p < 0.0001$) and were removed (items 1, 13, and 14). Item 22 displayed adequate fit to the model but its logit score (i.e. severity) was high (4.6). This item was removed to improve the targeting of this component (Figure E3).

SGRQ-I Impacts Component

Item 1: If you ever held a job:

- 1 = My lung condition interferes or made me stop work (new weight=83.3)
0 = My lung problem does not affect my job (new weight=0)

About your cough and shortness of breath

Item 2: Coughing hurts

- 1 = true (new weight=81.1)
0 = false (new weight=0)

Item 3: Coughing makes me tired

- 1 = true (new weight=79.1)
0 = false (new weight=0)

Item 4: Short of breath when I talk

- 1 = true (new weight=84.5)
0 = false (new weight=0)

Item 5: Short of breath when I bend over

- 1 = true (new weight=76.8)
0 = false (new weight=0)

Item 6: Cough or breathing disturbs my sleep

- 1 = true (new weight=87.9)
0 = false (new weight=0)

Item 7: I become exhausted easily

- 1 = true (new weight=84.0)
0 = false (new weight=0)

Other effects that your lung problem may have on you

Item 8: Embarrassing in public

1 = true (new weight=74.1)
0 = false (new weight=0)

Item 9: A nuisance to my family

1 = true (new weight=79.1)
0 = false (new weight=0)

Item 10: Panic or afraid

1 = true (new weight=87.7)
0 = false (new weight=0)

Item 11: Not in control

1 = true (new weight=90.1)
0 = false (new weight=0)

Item 12: Exercise is not safe for me

1 = true (new weight=75.7)
0 = false (new weight=0)

Item 13: Everything seems too much effort

1 = true (new weight=84.5)
0 = false (new weight=0)

How your breathing usually affects your daily life**Item 14: I cannot play sports**

1 = true (new weight=64.8)
0 = false (new weight=0)

Item 15: I cannot go out of the house to do grocery shopping

1 = true (new weight=81.0)
0 = false (new weight=0)

Item 16: I cannot do household chores

1 = true (new weight=79.1)
0 = false (new weight=0)

Item 17: I cannot move far from my bed or chair

1 = true (new weight=94.0)
0 = false (new weight=0)

Item 18: Which best describes how your breathing problem affects you

0 = does not stop me (new weight=0)
1 = stops one or two things (new weight=42.0)
2 = stops most things (new weight=84.2)
3 = stops me doing everything I would like to (new weight=96.7)

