4.12 DATA COLLECTION

The UK General Data Protection Regulation (GDPR) requires appropriate technical and organisational measures to be in place to implement the data protection principles effectively and safeguard individual rights. This is ‘data protection by design and by default’.

In essence, this means we will integrate or ‘bake in’ data protection into our processing activities and business practices, from the design stage right through the lifecycle.

4.12.1 Data to be collected:

- Weight
- Height
- Blood Test (blood biomarkers associated with the progression of the fibrosis)
- Blood Pressure
- QMVCT (Strength of the Quadriceps muscle measured in Newtons)
- mMRC (score of dyspnoea from 1 to 5)
- CPET (Maximum workload measured in watts)
- CWRCT (time or exercise tolerance measured in minutes)
- Physical activity levels in daily life (measured in steps)
- SGRQ (Score of this questionnaire that measures the QoL)
- HADS (Score of this questionnaire that measures anxiety and depression levels)

4.12.2 Time points for collection: these data will be collected during the baseline and post intervention appointment by the CI ([name]) and the PI ([name]) in Edinburgh and by [name] (Physiotherapist) in Newcastle.

4.12.3 Details of standardised tools to be used:

- Modified version of the Medical Research Council scale (mMRC): see appendix D.
- Saint George Respiratory Questionnaire (SGRQ): see appendix E.
- Hospital Anxiety Depression Scale (HADS): see appendix F.

4.12.4 Methods to maximise completeness of data: PI will call participants who have not returned questionnaires.

4.12.5 How will data be recorded Data will be recorded using both eCRF and pCRF.

4.12.6 Source Data Documentation: Source data is defined as all information in original records and certified copies of original records or clinical findings, observations, or other activities in a clinical study necessary for the reconstruction and evaluation of the study. Source data are contained in source documents.

Source documents are original documents, data and records where source data are recorded for the first time.

We will use the medical records from Trak to obtain information of the high resolution computed tomography (HRCT) of the thorax, echocardiograms, breathing tests including Spirometry, Lung volumes and DLCO.

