Appendix F:**Hospital Anxiety Depression Scale**

Instructions: Doctors are aware that emotions play an important part in most illnesses. If your doctor knows about these feelings he or she will be able to help you more. This questionnaire is designed to help your doctor know how you feel. Read each item and circle the reply which comes closest to how you have been feeling in the past week. Don't take too long over your replies: your immediate reaction to each item will probably be more accurate than a long thought out response.

I feel tense or 'wound up':	A	I feel as if I am slowed down:	D
Most of the time	3	Nearly all of the time	3
A lot of the time	2	Very often	2
Time to time, occasionally	1	Sometimes	1
Not at all	0	Not at all	0

I still enjoy the things I used to enjoy:	D	I get a sort of frightened feeling like 'butterflies in the stomach':	A
Definitely as much	0	Not at all	0
Not quite so much	1	Occasionally	1
Only a little	2	Quite often	2
Not at all	3	Very often	3

I get a sort of frightened feeling like something awful is about to happen:	A	I have lost interest in my appearance:	D
Very definitely and quite badly	3	Definitely	3
Yes, but not too badly	2	I don't take as much care as I should	2
A little, but it doesn't worry me	1	I may not take quite as much care	1
Not at all	0	I take just as much care as ever	0

I can laugh and see the funny side of things:	D	I feel restless as if I have to be on the move:	A
As much as I always could	0	Very much indeed	3
Not quite so much now	1	Quite a lot	2

Definitely not so much now	2	Not very much	1
Not at all	3	Not at all	0

Worrying thoughts go through my mind:	A	I look forward with enjoyment to things:	D
A great deal of the time	3	A much as I ever did	0
A lot of the time	2	Rather less than I used to	1
From time to time but not too often	1	Definitely less than I used to	3
Only occasionally	0	Hardly at all	2

I feel cheerful:	D	I get sudden feelings of panic:	A
Not at all	3	Very often indeed	3
Not often	2	Quite often	2
Sometimes	1	Not very often	1
Most of the time	0	Not at all	0

I can sit at ease and feel relaxed:	A	I can enjoy a good book or radio or TV programme:	D
Definitely	0	Often	0
Usually	1	Sometimes	1
Not often	2	Not often	2
Not at all	3	Very seldom	3

Questions relating to anxiety are indicated by an 'A' while those relating to depression are shown by a 'D'. Scores of 0-7 in respective subscales are considered normal, with 8-10 borderline and 11 or over indicating clinical 'caseness'

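### Two secondary-outcome scoring keys are misprinted (the SGRQ-I good-days item is reversed and one HADS depression item has two scores swapped), and the mMRC range is stated three ways

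*Protocol*

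**What the plan says.** Protocol section 3.2 names quality of life (SGRQ, IPF version), anxiety and depression (HADS) and dyspnoea (mMRC) as secondary outcomes. Section 4.12.3 refers the reader to Appendices D, E and F for these tools, and no other scoring source is named. Section 4.12.1 lists the SGRQ and HADS data as questionnaire scores.

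- **SGRQ-I (Appendix E, Symptoms).** The last item reads "Item 6: How often do you have good days". Its answers are keyed "2 = every day (new weight=93.3", then "1 = a few days (new weight=51.2", then 0 for none.
- **HADS (Appendix F).** The depression item on looking forward to things prints 0 and 1 for its two mildest answers, 3 for "Definitely less than I used to", and 2 for the last and most severe answer, *Hardly at all*.
- **mMRC.** Section 4.12.1 has "mMRC (score of dyspnoea from 1 to 5". The Appendix D heading says "this scale goes from 0 to 5". The form beneath that heading offers five boxes, graded 0 to 4.

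**The concern.** A summed score works only if every item points the same way. In the SGRQ-I as printed, more symptoms, more limitation and more impact all raise the score, and so does having more good days. A patient who improves on that item is recorded as deteriorating. Randomisation does not remove the problem: if one arm gains more good days, that arm is penalised more.

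The HADS swap makes the most severe answer to one depression item score as milder than the answer before it. The mMRC statements leave the range, and so the meaning of a recorded number, open to more than one reading.

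Quality of life is part of the research question in section 1.3, so a wrongly directed item there matters even though it is not the primary outcome.

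**Working it through.** The protocol states no figure to reproduce here. The check uses the printed keys alone, without an outside manual.

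**1. Direction of the SGRQ-I weights.** Appendix E prints 6 Symptoms, 10 Activities and 18 Impacts items, 34 in all. In 33 of them the best answer has weight 0 and the weight rises with worse status. For example, shortness of breath almost every day has "new weight=87.2", and not at all has 0. The good-days item alone gives 0 to the worst answer and the largest Symptoms weight to the best.

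**2. Size of the SGRQ-I error.** Assume score = 100 × sum of weights / maximum sum. The maximum weights are:

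- Symptoms: 80.6 + 76.8 + 87.2 + 86.2 + 66.2 + 93.3 = 490.3
- Activities (10 items): 744.5
- Impacts (18 items): 1483.5
- Total: 490.3 + 744.5 + 1483.5 = 2718.3

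The item's share is 93.3 / 490.3 = 19.0% of Symptoms and 93.3 / 2718.3 = 3.4% of the total.

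| Case | Symptoms score or change as printed | With the item reversed |
|---|---|---|
| No symptoms, good days every day | 93.3 / 490.3 → 19.0 | 0 |
| Every symptom at its worst, no good days | (490.3 − 93.3) / 490.3 → 81.0 | 100 |
| Change from none to every day | +19.0 (worse) | −19.0 (better) |
| Change from a few days to every day | (93.3 − 51.2) / 490.3 → +8.6 (worse) | −51.2 / 490.3 → −10.4 (better) |

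On the total score, the change from none to every day is +3.4 as printed and −3.4 when reversed.

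**3. HADS.** Taking the four printed scores of each of the 14 items in the order of their answers, 13 items run steadily 0 to 3 or 3 to 0. The exception is the looking-forward item, at 0, 1, 3, 2. In severity order its last two scores would be 2 and 3. As printed, the third answer is therefore 1 point too high and the fourth 1 point too low on the depression subscale (seven items scored 0 to 3, range 0 to 21).

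**4. mMRC.** Three ranges are given: 1 to 5, 0 to 5 and 0 to 4. The form's five grades, numbered 0 to 4, fit only the last.

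**The case against.** The best defence is that section 4.12.3 identifies the instruments and does not prescribe a scoring algorithm. Appendix E reads like reproduced instrument-development text and contains no aggregation formula, so the trial team may score with a validated program and never use these keys. That is possible, and it means a wrong result is not certain. But the protocol names no such program, and a printed key that contradicts itself should not stand.

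Several stronger readings are tempting, and the document does not support them:

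- *The trial's main result is at risk.* It is not. The primary outcome is endurance time on the constant work rate test (section 3.1), which uses none of these keys.
- *SGRQ-I Symptoms item 5 lacks a category and needs one.* Its two answers, more than one attack or none, leave exactly one attack unplaced. However, Appendix E says adjacent categories were collapsed for the Symptoms items, so two categories may be intended and the label may simply be loose. A new category would alter the instrument, and no weight for it is documented.
- *The two sites will code mMRC one grade apart.* Each box on the form carries its own grade, so staff would have to renumber it. An offset held constant within a site would also cancel from each patient's before–after change. This is an editorial inconsistency.
- *Patients will be misclassified on HADS.* One point can cross the printed boundaries at 7/8 or 10/11, but no endpoint in the protocol uses those categories.

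The HADS table was read from a PDF, so the source page should be checked. The other 13 items came through in order, which makes a reading error unlikely.

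**Conclusion.** The keys are wrong as written, for secondary outcomes only; they should be fixed before scoring. The reversed good-days item is the substantive error. It carries 19.0 of 100 Symptoms points and 3.4 of 100 total points under the assumed sum-over-maximum formula. That it runs in the wrong direction needs no formula, only the other 33 items. The HADS swap is worth 1 point on the depression subscale for a patient giving either affected answer, subject to the source page. The mMRC discrepancy is minor. The corrected values are inferred from internal consistency and need confirming against the instruments themselves.

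**What to change.** 1. In Appendix E, reverse the good-days item: none = 93.3, a few days = 51.2, every day = 0, with the codes 2, 1, 0 following the weights.
2. In Appendix F, score the third answer of the looking-forward item 2 and *Hardly at all* 3.
3. State the mMRC range as 0 to 4 in section 4.12.1 and in the Appendix D heading.
4. Before any scoring, check every key against the licensed instruments. Include the answer labels of SGRQ-I Symptoms item 5, to establish where exactly one attack belongs, without adding a category.
5. Keep item-level answers in the database as well as the summed scores, and re-score if any scoring has already been done.

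The cost is a correction to three appendices, one line of section 4.12.1 and the CRF or database coding, plus entry of item-level answers if only totals were planned. Patients are not affected.

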Appendix F:**Hospital Anxiety Depression Scale**

Instructions: Doctors are aware that emotions play an important part in most illnesses. If your doctor knows about these feelings he or she will be able to help you more. This questionnaire is designed to help your doctor know how you feel. Read each item and circle the reply which comes closest to how you have been feeling in the past week. Don't take too long over your replies: your immediate reaction to each item will probably be more accurate than a long thought out response.

I feel tense or 'wound up':	A	I feel as if I am slowed down:	D
Most of the time	3	Nearly all of the time	3
A lot of the time	2	Very often	2
Time to time, occasionally	1	Sometimes	1
Not at all	0	Not at all	0

I still enjoy the things I used to enjoy:	D	I get a sort of frightened feeling like 'butterflies in the stomach':	A
Definitely as much	0	Not at all	0
Not quite so much	1	Occasionally	1
Only a little	2	Quite often	2
Not at all	3	Very often	3

I get a sort of frightened feeling like something awful is about to happen:	A	I have lost interest in my appearance:	D
Very definitely and quite badly	3	Definitely	3
Yes, but not too badly	2	I don't take as much care as I should	2
A little, but it doesn't worry me	1	I may not take quite as much care	1
Not at all	0	I take just as much care as ever	0

I can laugh and see the funny side of things:	D	I feel restless as if I have to be on the move:	A
As much as I always could	0	Very much indeed	3
Not quite so much now	1	Quite a lot	2

Definitely not so much now	2	Not very much	1
Not at all	3	Not at all	0

Worrying thoughts go through my mind:	A	I look forward with enjoyment to things:	D
A great deal of the time	3	A much as I ever did	0
A lot of the time	2	Rather less than I used to	1
From time to time but not too often	1	Definitely less than I used to	3
Only occasionally	0	Hardly at all	2

I feel cheerful:	D	I get sudden feelings of panic:	A
Not at all	3	Very often indeed	3
Not often	2	Quite often	2
Sometimes	1	Not very often	1
Most of the time	0	Not at all	0

I can sit at ease and feel relaxed:	A	I can enjoy a good book or radio or TV programme:	D
Definitely	0	Often	0
Usually	1	Sometimes	1
Not often	2	Not often	2
Not at all	3	Very seldom	3

Questions relating to anxiety are indicated by an 'A' while those relating to depression are shown by a 'D'. Scores of 0-7 in respective subscales are considered normal, with 8-10 borderline and 11 or over indicating clinical 'caseness'

